5.2.2 Serious Adverse Events (Immediately Reportable to the Sponsor)

A serious adverse event is any adverse event that meets any of the following criteria:

- Fatal (i.e., the adverse event actually causes or leads to death)

- Life threatening (i.e., the adverse event, in the view of the investigator, places the patient at immediate risk of death)
 - This does not include any adverse event that had it occurred in a more severe form or was allowed to continue might have caused death.
- Requires or prolongs inpatient hospitalization (see [Section 5.3.5.10](#))
- Results in persistent or significant disability/incapacity (i.e., the adverse event results in substantial disruption of the patient's ability to conduct normal life functions)
- Congenital anomaly/birth defect in a neonate/infant born to a mother exposed to study drug
- Significant medical event in the investigator's judgment (e.g., may jeopardize the patient or may require medical/surgical intervention to prevent one of the outcomes listed above)

The terms "severe" and "serious" are not synonymous. Severity refers to the intensity of an adverse event (e.g., rated as mild, moderate, or severe, or according to Division of AIDS Table for Grading the Severity of Adult and Pediatric Adverse Events (DAIDS); see [Section 5.3.3](#), [Appendix 8](#), and [Appendix 9](#)); the event itself may be of relatively minor medical significance (such as severe headache without any further findings).

Severity and seriousness need to be independently assessed for each adverse event recorded on the eCRF.

Serious adverse events are required to be reported by the investigator to the Sponsor immediately (i.e., no more than 24 hours after learning of the event; see [Section 5.4.2](#) for reporting instructions).

5.2.3 Non-Serious Adverse Events of Special Interest (Immediately Reportable to the Sponsor)

Non-serious adverse events of special interest (AESI) are required to be reported by the investigator to the Sponsor immediately (i.e., no more than 24 hours after learning of the event; see [Section 5.4.2](#) for reporting instructions). Adverse events of special interest for this study include the following:

- Cases of potential drug-induced liver injury that include an elevated ALT or AST in combination with either an elevated bilirubin or clinical jaundice, as defined by Hy's law (see [Section 5.3.5.6](#))
- Suspected transmission of an infectious agent by the study drug, as defined below
 - Any organism, virus, or infectious particle (e.g., prion protein transmitting transmissible spongiform encephalopathy), pathogenic or non-pathogenic, is considered an infectious agent. A transmission of an infectious agent may be suspected from clinical symptoms or laboratory findings that indicate an infection in a patient exposed to a medicinal product. This term applies only when a contamination of the study drug is suspected.

- Adverse events associated with suspected cases of infusion-related reactions (IRR) which occur within 24 hours of study drug administration and may show the following signs and symptoms (for guidance on reporting AEs associated with IRR, see [Section 5.3.5.1](#) below):
 - Fever and/or shaking chills
 - Flushing and/or itching
 - Alterations in heart rate and blood pressure
 - Dyspnea or chest discomfort
 - Back or abdominal pain
 - Nausea, vomiting, and/or diarrhea
 - Various types of skin rashes
 - Anaphylaxis
- Anaphylaxis due to IV drugs most often presents with the following signs and symptoms:
 - Cutaneous symptoms: flushing, itching, urticaria, and/or angioedema (usually of face, eyelids, or lips)
 - Respiratory symptoms: repetitive cough, sudden nasal congestion, shortness of breath, chest tightness, wheeze, sensation of throat closure or choking, and or change in voice quality due to laryngeal edema
 - Cardiovascular symptoms: faintness, tachycardia (or less often bradycardia), tunnel vision, chest pain, hypotension, sense of impending doom, and/or loss of consciousness
 - Gastrointestinal symptoms: such as nausea, vomiting, abdominal cramping, and diarrhea

5.3 METHODS AND TIMING FOR CAPTURING AND ASSESSING SAFETY PARAMETERS

The investigator is responsible for ensuring that all adverse events (see [Section 5.2.1](#) for definition) are recorded on the Adverse Event eCRF and reported to the Sponsor in accordance with instructions provided in this section and in [Section 5.4 – 5.6](#).

For each adverse event recorded on the Adverse Event eCRF, the investigator will make an assessment of seriousness (see [Section 5.2.2](#) for seriousness criteria), severity (see [Section 5.3.3](#)), and causality (see [Section 5.3.4](#)).

5.3.1 Adverse Event Reporting Period

Investigators will seek information on adverse events at each patient contact. All adverse events, whether reported by the patient or noted by study personnel, will be recorded in the patient’s medical record and on the Adverse Event eCRF.

After informed consent has been obtained **but prior to initiation of study drug**, only serious adverse events caused by a protocol-mandated intervention (e.g., invasive procedures such as biopsies, discontinuation of medications) should be reported (see [Section 5.4.2](#) for instructions for reporting serious adverse events).

After initiation of study drug, all adverse events, regardless of relationship to study drug, will be reported until the Day 60 visit or Early Discontinuation visit. After this period, the investigator is not required to actively monitor patients for adverse events; however, the Sponsor should be notified if the investigator becomes aware of any death or other serious adverse event that occurs after discharge, regardless of causality. The Sponsor should also be notified if the investigator becomes aware of a congenital anomaly/birth defect in a subsequently conceived offspring of a female patient exposed to study drug (see [Section 5.6](#)).

5.3.2 Eliciting Adverse Event Information

A consistent methodology of non-directive questioning should be adopted for eliciting adverse event information at all patient evaluation timepoints. Examples of non-directive questions include the following:

"How have you felt since your last clinic visit?"

"Have you had any new or changed health problems since you were last here?"

5.3.3 Assessment of Severity of Adverse Events

Investigators will seek information on adverse events and serious adverse events at each patient contact. All AEs, and SAEs, whether reported by the patient or noted by authorized study personnel, will be recorded.

The adverse event grading (severity) scale in the DAIDS v1.0 will be used for assessing AE severity (see [Table 5](#)).

Table 5 Adverse Event Grading (Severity) Scale

PARAMETER	GRADE 1 MILD	GRADE 2 MODERATE	GRADE 3 SEVERE	GRADE 4 POTENTIALLY LIFE- THREATENING
ESTIMATING SEVERITY GRADE				
Clinical AE NOT identified elsewhere in this DAIDS AE Grading Table	Symptoms causing no or minimal interference with usual social and functional activities	Symptoms causing greater than minimal interference with usual social & functional activities	Symptoms causing inability to perform usual social & functional activities	Symptoms causing inability to perform basic self-care functions OR Medical or operative intervention indicated to prevent permanent impairment, persistent disability, or death

5.3.4 Assessment of Causality of Adverse Events

Investigators should use their knowledge of the patient, the circumstances surrounding the event, and an evaluation of any potential alternative causes to determine whether or not an adverse event is considered to be related to the study drug, indicating "yes" or "no" accordingly. The following guidance should be taken into consideration (see also [Table 6](#)):

- Temporal relationship of event onset to the initiation of study drug
- Course of the event, considering especially the effects of dose reduction, discontinuation of study drug, or reintroduction of study drug (as applicable)
- Known association of the event with the study drug or with similar treatments
- Known association of the event with the disease under study
- Presence of risk factors in the patient or use of concomitant medications known to increase the occurrence of the event
- Presence of non-treatment-related factors that are known to be associated with the occurrence of the event

Table 6 Causal Attribution Guidance

Is the adverse event suspected to be caused by the study drug on the basis of facts, evidence, science-based rationales, and clinical judgment?	
YES	There is a plausible temporal relationship between the onset of the adverse event and administration of the study drug, and the adverse event cannot be readily explained by the patient's clinical state, intercurrent illness, or concomitant therapies; and/or the adverse event follows a known pattern of response to the study drug; and/or the adverse event abates or resolves upon discontinuation of the study drug or dose reduction and, if applicable, reappears upon re-challenge.
NO	An adverse event will be considered related, unless it fulfills the criteria specified below. Evidence exists that the adverse event has an etiology other than the study drug (e.g., pre-existing medical condition, underlying disease, intercurrent illness, or concomitant medication); and/or the adverse event has no plausible temporal relationship to administration of the study drug (e.g., chronic obstructive pulmonary disease [COPD] diagnosed 2 days after first dose of study drug).

For patients receiving combination therapy, causality will be assessed individually for each protocol-mandated therapy.

5.3.5 Procedures for Recording Adverse Events

Investigators should use correct medical terminology/concepts when recording adverse events on the Adverse Event eCRF. Avoid colloquialisms and abbreviations.

Only one adverse event term should be recorded in the event field on the Adverse Event eCRF.

5.3.5.1 Diagnosis versus Signs and Symptoms Infusion-Related Reactions

Adverse events that occur during or within 24 hours after study drug infusion should be captured as individual signs and symptoms rather than a diagnosis of allergic reaction or infusion reaction.

Other Adverse Events

For adverse events other than infusion-related reactions, a diagnosis (if known) should be recorded on the Adverse Event eCRF rather than individual signs and symptoms (e.g., record only liver failure or hepatitis rather than jaundice, asterix, and elevated transaminases). However, if a constellation of signs and/or symptoms cannot be medically characterized as a single diagnosis or syndrome at the time of reporting, each individual event should be recorded on the Adverse Event eCRF. If a diagnosis is subsequently established, all previously reported adverse events based on signs and symptoms should be nullified and replaced by one adverse event report based on the single diagnosis, with a starting date that corresponds to the starting date of the first symptom of the eventual diagnosis.

5.3.5.2 Adverse Events That Are Secondary to Other Events

In general, adverse events that are secondary to other events (e.g., cascade events or clinical sequelae) should be identified by their primary cause, with the exception of severe or serious secondary events. A medically significant secondary adverse event that is separated in time from the initiating event should be recorded as an independent event on the Adverse Event eCRF. For example:

- If vomiting results in mild dehydration with no additional treatment in a healthy adult, only vomiting should be reported on the eCRF.
- If vomiting results in severe dehydration, both events should be reported separately on the eCRF.
- If a severe gastrointestinal hemorrhage leads to renal failure, both events should be reported separately on the eCRF.
- If dizziness leads to a fall and consequent fracture, all three events should be reported separately on the eCRF.
- If neutropenia is accompanied by an infection, both events should be reported separately on the eCRF.

All adverse events should be recorded separately on the Adverse Event eCRF if it is unclear as to whether the events are associated.

5.3.5.3 Persistent or Recurrent Adverse Events

A persistent adverse event is one that extends continuously, without resolution, between patient evaluation timepoints. Such events should only be recorded once on the Adverse Event eCRF, unless the severity increases. If a persistent adverse event becomes more severe, it should be recorded as a separate event on the Adverse Event

eCRF. The initial (less severe) adverse event report should be updated to indicate that the event resolved on the date just prior to the day the event became more severe. If a persistent adverse event becomes serious, it should be recorded as a separate event on the Adverse Event eCRF and reported to the Sponsor immediately (i.e., no more than 24 hours after learning that the event became serious; see [Section 5.4.2](#) for reporting instructions). The initial (non-serious) adverse event report should be updated to indicate that the event resolved on the date just prior to the day the event became serious.

A recurrent adverse event is one that resolves between patient evaluation timepoints and subsequently recurs. Each recurrence of an adverse event should be recorded as a separate event on the Adverse Event eCRF.

5.3.5.4 Abnormal Laboratory Values

Not every laboratory abnormality qualifies as an adverse event. A laboratory test result must be reported as an adverse event if it meets any of the following criteria:

- Accompanied by clinical symptoms
- Results in a change in study treatment (e.g., dosage modification, treatment interruption, or treatment discontinuation)
- Results in a medical intervention (e.g., potassium supplementation for hypokalemia) or a change in concomitant therapy
- Clinically significant in the investigator's judgment (laboratory abnormalities should be repeated at the first opportunity and only considered clinically significant if they persist on repeat assessment)

It is the investigator's responsibility to review all laboratory findings. Medical and scientific judgment should be exercised in deciding whether an isolated laboratory abnormality should be classified as an adverse event.

If a clinically significant laboratory abnormality is a sign of a disease or syndrome (e.g., alkaline phosphatase and bilirubin 5× upper limit of normal [ULN] associated with cholestasis), only the diagnosis (i.e., cholestasis) should be recorded on the Adverse Event eCRF.

If a clinically significant laboratory abnormality is not a sign of a disease or syndrome, the abnormality itself should be recorded on the Adverse Event eCRF, along with a descriptor indicating if the test result is above or below the normal range (e.g., "elevated potassium," as opposed to "abnormal potassium"). If the laboratory abnormality can be characterized by a precise clinical term per standard definitions, the clinical term should be recorded as the adverse event. For example, an elevated serum potassium level of 7.0 mEq/L should be recorded as "hyperkalemia."

Observations of the same clinically significant laboratory abnormality from visit to visit should not be repeatedly recorded on the Adverse Event eCRF, unless the etiology changes. The initial severity of the event should be recorded, and the severity or seriousness should be updated any time the event worsens.

5.3.5.5 Abnormal Vital Sign Values

Not every vital sign abnormality qualifies as an adverse event. A vital sign result must be reported as an adverse event if it meets any of the following criteria:

- Accompanied by clinical symptoms
- Results in a change in study treatment (e.g., dosage modification, treatment interruption, or treatment discontinuation)
- Results in a medical intervention or a change in concomitant therapy
- Clinically significant in the investigator's judgment. Abnormal vital sign values should be repeated at the first opportunity and only considered clinically significant if they persist on repeat assessment)

It is the investigator's responsibility to review all vital sign findings. Medical and scientific judgment should be exercised in deciding whether an isolated vital sign abnormality should be classified as an adverse event.

If a clinically significant vital sign abnormality is a sign of a disease or syndrome (e.g., high blood pressure), only the diagnosis (i.e., hypertension) should be recorded on the Adverse Event eCRF.

Observations of the same clinically significant vital sign abnormality from visit to visit should not be repeatedly recorded on the Adverse Event eCRF, unless the etiology changes. The initial severity of the event should be recorded, and the severity or seriousness should be updated any time the event worsens.

5.3.5.6 Abnormal Liver Function Tests

The finding of an elevated ALT or AST ($>3 \times$ baseline value) in combination with either an elevated total bilirubin ($>2 \times$ ULN) or clinical jaundice in the absence of cholestasis or other causes of hyperbilirubinemia is considered to be an indicator of severe liver injury. Therefore, investigators must report as an adverse event the occurrence of either of the following:

- Treatment-emergent ALT or AST $>3 \times$ baseline value in combination with total bilirubin $>2 \times$ ULN (of which $\geq 35\%$ is direct bilirubin)
- Treatment-emergent ALT or AST $>3 \times$ baseline value in combination with clinical jaundice

The most appropriate diagnosis or (if a diagnosis cannot be established) the abnormal laboratory values should be recorded on the Adverse Event eCRF (see [Section 5.3.5.1](#)) and reported to the Sponsor immediately (i.e., no more than 24 hours after learning of

the event) either as a serious adverse event or a non-serious adverse event of special interest (see [Section 5.4.2](#)).

5.3.5.7 Deaths

For this protocol, mortality is an efficacy endpoint. Deaths that occur during the protocol-specified adverse event reporting period (see [Section 5.3.1](#)) that are attributed by the investigator solely to progression of severe influenza or any related co-morbidities should be recorded on the Study Completion/Early Discontinuation eCRF. All other on-study deaths, regardless of relationship to study drug, must be recorded on the Adverse Event eCRF, and immediately reported to the Sponsor as an SAE (see [Section 5.4.2](#)).

Death should be considered an outcome and not a distinct event. The event or condition that caused or contributed to the fatal outcome should be recorded as the single medical concept on the Adverse Event eCRF. Generally, only one such event should be reported. The term "**sudden death**" should be used only for the occurrence of an abrupt and unexpected death due to presumed cardiac causes in a patient with or without pre-existing heart disease, within 1 hour after the onset of acute symptoms or, in the case of an unwitnessed death, within 24 hours after the patient was last seen alive and stable. If the cause of death is unknown and cannot be ascertained at the time of reporting, "**unexplained death**" should be recorded on the Adverse Event eCRF. If the cause of death later becomes available (e.g., after autopsy), "unexplained death" should be replaced by the established cause of death.

5.3.5.8 Pre-existing Medical Conditions

A pre-existing medical condition is one that is present at the screening visit for this study. Such conditions should be recorded on the General Medical History and Baseline Conditions eCRF.

A pre-existing medical condition should be recorded as an adverse event only if the frequency, severity, or character of the condition worsens during the study. When recording such events on the Adverse Event eCRF, it is important to convey the concept that the pre-existing condition has changed by including applicable descriptors (e.g., "more frequent headaches").

5.3.5.9 Lack of Efficacy or Worsening of Influenza A Infection

Medical occurrences or symptoms of deterioration that are anticipated as part of influenza A should only be recorded as an adverse event if judged by the investigator to have unexpectedly worsened in severity or frequency or changed in nature at any time during the study. When recording an unanticipated worsening of influenza A on the Adverse Event eCRF, it is important to convey the concept that the condition has changed by including applicable descriptors (e.g., "accelerated influenza A").

5.3.5.10 Hospitalization or Prolonged Hospitalization

Any adverse event that results in hospitalization following initial discharge (i.e., in-patient admission to a hospital) or prolonged hospitalization (after the current study hospitalization) should be documented and reported as a serious adverse event (per the definition of serious adverse event in [Section 5.2.2](#)), except as outlined below.

The following hospitalization scenarios are not considered to be adverse events:

- Hospitalization for respite care
- Hospitalization for a pre-existing condition, provided that all of the following criteria are met:

The hospitalization was planned prior to the study or was scheduled during the study when elective surgery became necessary because of the expected normal progression of the disease

The patient has not experienced an adverse event

The following hospitalization scenarios are not considered to be serious adverse events, but should be reported as adverse events instead:

- Hospitalization that was necessary because of patient requirement for outpatient care outside of normal outpatient clinic operating hours

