1. BACKGROUND

1.1 BACKGROUND ON INFLUENZA

Influenza A is a membrane-enveloped RNA virus that causes significant morbidity and mortality. Currently, there is a great need in hospitalized influenza patients for a parenteral therapeutic option that is well tolerated, can rapidly resolve influenza-related signs and symptoms, decrease mortality, reduce hospital and intensive care unit (ICU) stays, as well as have a prolonged window for initiation of treatment beyond the current standard of care (i.e., within 48 hours of the onset of flu symptoms).

Approximately 200,000 to 278,000 patients are hospitalized with severe influenza infections annually in the United States (U.S.) (Thompson et al. 2004; Zhou et al. 2012), and assuming the same rate reported in the U.S., an estimated 319,000 to 445,000 patients are hospitalized in the European Union (E.U.). Hospitalization due to severe influenza is associated with high mortality (4%–8%), ICU admission (5%–17%; Lee and Ison 2012), mechanical ventilation support in an ICU setting (7%–11%; Doshi et al. 2011), and prolonged hospital stays (5–9 days; Lee and Ison 2012). During a pandemic season, the outcomes may be more serious, with up to 34% of patients requiring ICU care and a mortality rate as high as 15% (Lee and Ison 2012).

Influenza infection is an upper and lower respiratory disease with a broad spectrum of presentations that can result in fever, shortness-of-breath, pneumonia, respiratory failure, secondary respiratory infections, and even death. The standard of care therapy for patients hospitalized with influenza consists of supportive measures and administration of available antiviral agents, primarily neuraminidase inhibitors (NAI) that include but are not limited to oseltamivir, zanamivir, and peramivir. However, a significant unmet medical need still exists in the severely ill patient population, as evidenced by the considerable degree of morbidity and mortality in this setting. To address this need, Genentech Inc. /F.Hoffmann-La Roche Ltd. (Genentech) is developing a highly-specific anti-influenza A (MHAA4549A) antibody therapy for treatment of hospitalized patients with severe influenza.

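### Section 5.3.5.10 reads as narrower than Section 5.2.2 on prolonged hospitalization, so adverse events that lengthen the index stay may be classified inconsistently

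*Combined protocol and SAP*

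**What the plan says.** Section 5.2.2 lists the seriousness criteria. Its hospitalization criterion is "Requires or prolongs inpatient hospitalization". It has no exclusion for the admission in which the patient is dosed, and it refers the reader to Section 5.3.5.10. The other criteria relevant during the stay are fatal, life-threatening and disabling events, and "Significant medical event in the investigator's judgment".

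Section 5.3.5.10 gives the instruction in two limbs. The first is an adverse event leading to in-patient admission after the initial discharge. The second is "prolonged hospitalization (after the current study hospitalization) should be documented and reported as a serious adverse event". The same sentence points back to Section 5.2.2 for what counts as serious and makes the rule subject to listed exceptions. Respite care and certain planned admissions for a pre-existing condition are not adverse events at all. One scenario is downgraded from serious to non-serious: "Hospitalization that was necessary because of patient requirement for outpatient care outside of normal outpatient clinic operating hours". Lengthening of the study admission is not among the exceptions.

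Section 5.3.1, in Versions 2 and 3, says: "After initiation of study drug, all adverse events, regardless of relationship to study drug, will be reported until the Day 60 visit". The period ends sooner for a patient who leaves the study early, and the original protocol uses Day 30. Section 5.4 confines 24-hour reporting to serious adverse events, non-serious adverse events of special interest and pregnancies.

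The conflicting wording of 5.2.2 and 5.3.5.10 is the same in the original protocol, Version 2 and Version 3 (VHP Only). Of Version 5 (Global), the supplied text contains only the cover page and the start of the amendment rationale, not Section 5.

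**The concern.** Section 4.1.1 enrols hospitalized patients, and Appendix 1a keeps them in hospital for at least 24 hours after dosing. Until discharge a patient cannot be newly admitted, so prolongation is the only way the hospitalization criterion can be met. If the second limb of 5.3.5.10 excludes the study admission, that criterion does not operate between dosing and discharge.

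Take a kidney injury or an arrhythmia that is not life-threatening or disabling but adds days to the stay. Under that reading it becomes serious only if the investigator judges it medically significant. The special-interest list in Section 5.2.3 would not catch it: the list covers potential drug-induced liver injury, suspected infusion-related reactions including anaphylaxis, and suspected transmission of an infectious agent.

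Two things are at stake. One is 24-hour notice to the sponsor. The other is the meaning of the serious-event count, whose frequency is part of the safety objective in Section 2.1 and which is pooled over about 170 centers (Section 3.1.1). Earlier clinical experience is in 122 healthy volunteers (Section 1.2.2 in Versions 2 and 3), so events in severely ill inpatients are new information.

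**Working it through.** The plan states no figure on this point. The check is a comparison of the texts, followed by one calculation on timing.

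**1. One event under each section.** Take an adverse event after dosing that lengthens the study admission. Suppose it is not fatal, life-threatening or disabling, is not judged medically significant, and is not of special interest.

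| Rule applied | Serious? | 24-hour report under 5.4? |
|---|---|---|
| 5.2.2 as written | Yes | Yes |
| 5.3.5.10, first limb | No: no discharge yet | No |
| 5.3.5.10, second limb, taken to mean a hospitalization after the study admission | No | No |
| 5.3.5.10, second limb, taken to mean a stay extended past what the study admission required | Yes | Yes |

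The outcome depends on which section the site follows and how it reads the bracketed phrase.

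**2. Whether the cross-reference settles it.** Section 5.2.2 sends the hospitalization criterion to 5.3.5.10, and 5.3.5.10 says it applies the definition in 5.2.2. Each defers to the other. A site looking for the specific rule ends at 5.3.5.10, where the time limits are.

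**3. How much of the treatment period lies in the index stay.** Inputs:
- Section 1.3.2.4 equates 120 days with about 5 half-lives, so half-life = 120 / 5 = 24 days.
- Section 1.1 gives "prolonged hospital stays (5–9 days"). This is for hospitalized severe influenza generally.
- Assumption: mono-exponential decline, so share of total AUC by day t = 1 − 2^(−t / half-life).

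Results:

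| Half-life | Day 1 | Day 5 | Day 9 | Day 30 |
|---|---|---|---|---|
| 12 days | 6% | 25% | 41% | 82% |
| 18 days | 4% | 18% | 29% | 69% |
| 24 days (documents) | 3% | 13% | 23% | 58% |
| 30 days | 2% | 11% | 19% | 50% |

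The table counts days from dosing. Dosing may fall up to 48 hours after admission, so a 5-day stay can leave as little as 5 − 2 = 3 days after dosing. At a 24-day half-life the share is then 1 − 2^(−3/24) = 8%.

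What does fall inside a typical index stay is the infusion, its 24-hour reaction window, the peak serum level and most of the 5-day minimum oseltamivir course. Most systemic antibody exposure comes after discharge.

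**The case against.** The strongest case against the point is that the definition itself is sound. It is in 5.2.2, it covers prolongation without restriction, and 5.3.5.10 says it is applying that definition. The word *only* does not appear in 5.3.5.10, and its exceptions omit index-stay prolongation. The bracketed phrase may have been meant as a stay extended beyond what the study admission required. The structure gives that reading some support: taken narrowly, the second limb adds little to the first, since a later hospitalization caused by an adverse event is already covered. This stands as an argument about intent. It does not remove the problem, because the narrower reading is closer to the words and nothing in the section tells a site to prefer the other.

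It is also fair that little would go unrecorded. All adverse events are collected to the end of follow-up. Section 5.1 (Versions 2 and 3) provides ongoing blinded review by the Medical Monitor and a drug safety scientist, and regular unblinded review by the two committees. Fatal, life-threatening, disabling and medically significant events remain serious during the stay (with the separate rule in 5.3.5.7 for deaths attributed solely to influenza or related co-morbidities), and suspected infusion reactions within 24 hours are reported at once as events of special interest. That stands, and it limits the issue to classification and speed of reporting for a residual group.

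A reader might infer that nearly all drug exposure falls within the index stay. The 13% to 23% of AUC by days 5 to 9 contradicts this. A reader might also take the Phase 2a transaminase and amylase elevations, seen within the first 2 weeks, as examples of what would be missed. They were transient findings in healthy challenge volunteers and are not evidence of prolonged hospitalization.

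**Conclusion.** The point holds as an internal inconsistency. In the three versions whose Section 5 is supplied, 5.3.5.10 reads as narrower than 5.2.2, and an event that lengthens the index admission can be classified either way.

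Its size cannot be estimated: the documents give no expected number of events that prolong the stay, meet no other criterion and are not of special interest. Two larger conclusions are not supported. A reader might infer that such events lie outside the serious-event definition; they do not, because 5.2.2 includes them, and what excludes them is one reading of the reporting instruction. A reader might also infer that all 334 planned patients are affected. The wording governs all of them but matters only for those who have such an event.

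In Versions 2 and 3 randomization is 1:1, double-blind and stratified by site (Section 4.2), so differing site practice should affect both arms similarly. The expected result is a lower and less consistent serious-event count and slower notice for some events, rather than a tilt toward one arm.

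The conclusion rests on the natural reading of the bracketed phrase, on sites following the specific section over the general criterion, and on the wording having survived into Version 5 (Global), which cannot be confirmed here.

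**What to change.** First confirm whether the bracketed phrase is still in Section 5.3.5.10 of Version 5 (Global). If it is, reconcile the section with 5.2.2 in one of two ways, keeping the listed exceptions:

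- delete the bracketed phrase; or
- replace the sentence with: *An adverse event that, in the investigator's judgment, extends the current study hospitalization beyond the stay expected for the influenza itself, or that leads to hospitalization after initial discharge, is reported as a serious adverse event.*

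The second is preferable because it tells sites what the stay is to be compared with. It also fits Section 5.3.5.9, under which anticipated deterioration from influenza is not recorded as an adverse event unless it unexpectedly worsens or changes in nature. A long stay due to influenza alone would therefore not trigger a report.

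The cost is one sentence in the next amendment, a memo to sites, and some additional serious-event reports during the index admission. The second option also leaves a judgment about the expected length of stay, which sites will not make identically.
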